1.0 Objectives / Specific Aims

The overall objective of this double blind, sham controlled study is to evaluate the feasibility, tolerability, and preliminary efficacy of using a single day accelerated course of repetitive transcranial magnetic stimulation (rTMS) to decrease smoking cue induced nicotine craving in smokers.

- Aim 1: Determine if the delivery of a course of five rTMS sessions during a single day is feasible and well tolerated in participants with nicotine use disorder. We will test the hypothesis that greater than 75% of participants who start the rTMS course will complete the 5 treatments, and greater than 75% of participants will tolerate a treatment dose of greater than 100% rMT.
- Aim 2: Determine if nicotine dependent participants will experience a decrease in cue induced nicotine craving after 5 sessions of rTMS. We hypothesize that participants receiving active rTMS will have a greater decrease in cue induced nicotine craving after a five session treatment course of active rTMS when compared to those participants receiving sham rTMS.

2.0 Background

Despite widespread knowledge of the dangers of tobacco smoke, smoking remains the leading cause of preventable death in the world, leading to approximately 6 million deaths a year [1]. In addition, tobacco smoking has a profound economic cost to society with direct medical costs of 170 billion dollars a year attributed to smoking [2]. In 2015, 68% of smokers reported a desire to quit and each year approximately 55% of smokers make a quit attempt, demonstrating that the majority of smokers wish to quit and are willing to attempt quitting [3]. There are several available interventions to increase the success rate of a quit attempt including counseling, quit-lines, nicotine replacement therapy, bupropion and varenicline. However, despite the desire to quit and several available smoking cessation aids available, only 7.4% of smokers were able to quit in 2015 [4] which demonstrates a need for novel smoking cessation interventions.

As nicotine is the primary psychoactive compound in tobacco smoke, nicotine craving is modified by smoking cessation interventions such as nicotine replacement therapy, bupropion and varenicline[5]. Similarly to other drugs of abuse, nicotine activates mesolimbic dopamine pathways in the brain[6]. Another area of interest in addictions is the function of the dorsolateral prefrontal cortex (DLPFC) which has been found to be important in processing craving for nicotine [7] and other substances such as alcohol[8]. This has led to interest in developing new addictions treatments through decreasing substance craving by non-invasive stimulation of relevant brain regions using repetitive transcranial magnetic stimulation (rTMS). rTMS involves the delivery of magnetic pulses through the scalp to alter cortical excitability. The application of rTMS to the DLPFC is an effective, safe, non-invasive treatment currently FDA approved for the treatment of Major Depressive Disorder [9, 10]. A recent review outlined 19 studies that have used rTMS to modify craving for nicotine, alcohol and cocaine [11]. A single session of stimulatory rTMS of the left DLPFC has demonstrated a decrease in cue induced nicotine craving [12] and a series of 10 sessions stimulating the DLPFC has been demonstrated to decrease smoking[13]. Additionally, a recent randomized controlled trial has further demonstrated clinical significance by using rTMS to induce smoking cessation in nicotine dependent individuals with 6-month abstinence rates of 33% for the active intervention compared to only 9% abstinence in the sham condition[14]. Further trials of rTMS for smoking cessation are ongoing or nearing completion.

One drawback of current rTMS treatment protocols is the several week course of daily treatment sessions. In the case of depression, a typical treatment protocol is daily treatments for 4-6 weeks providing 3,000 pulses a day[15]. In addictions, the course is less defined and a recent smoking cessation trial used daily treatments of 990 pulses for 2 weeks, plus three additional treatments during the third week[14]. There is evidence to suggest that the total number of rTMS pulses delivered may mediate the treatment response[16], raising the possibility of shortening treatment courses by delivering more pulses in a day. Several studies have demonstrated the safety and possible efficacy of delivering multiple treatment sessions in day for the treatment of depression. For example, improvement in both depression and anxiety has been demonstrated through the administration of 15 rTMS sessions for a total of 15,000 pulses over the course of two days [17]. Additionally, the safety of delivering 6,000 rTMS pulses three times daily for a total of 54,000 pulses in a 3-day course was well tolerated with a retention rate of 88%, and demonstrated a trend towards a more rapid decline in suicidality [18]. A recent feasibility study has begun to examine the impact of accelerated rTMS on alcohol relapse neuropathways [19]. Despite the promise of rTMS as a possible treatment for smoking cessation, and the promise of accelerated rTMS paradigms in reducing the duration, and patient burden of delivering rTMS, there have not yet been investigations using accelerated rTMS for smoking cessation. We subsequently propose to take the first step in developing an accelerated rTMS paradigm in smokers.

2.0 Intervention to be studied

Study Intervention: Left dorsolateral pre-frontal cortex (LDLPFC) rTMS stimulation with parameters of each session delivering 3000 pulses of up to110% motor threshold 10hz stimulation, 5 seconds on 10 seconds off. The accelerated course will consist of 5 sessions delivered during a single day for a total of 15,000 pulses.

Control: Sham sessions will be delivered using an electronic sham system consisting of a coil that mimics the appearance and sound of TMS, combined with a transcutaneous electrical nerve stimulation (TENS) device which produces a small electric shock mimicking the feeling of real TMS. This type of sham has been demonstrated to be indistinguishable from active TMS, has been well tolerated in [9, 18], and successfully used in other clinical trials[20, 21].

3.0 Study Endpoints:

Aim 1: Determine if the delivery of a course of five rTMS sessions during a single day is feasible and well tolerated in participants with nicotine use disorder. Primary endpoint will be the percent of participants starting the rTMS treatment who complete all 5 rTMS treatments in a single day.

Aim 2: Determine if nicotine dependent participants will experience a decrease in cue induced nicotine craving after 5 sessions of rTMS. Primary endpoint of difference in 0-100 averaged pre and post treatment smoking cue induced cigarette craving scores using an adopted QSU- B 10 questionnaire to measure smoking craving [12]. A secondary endpoint will be the trend of level of neutral cigarette craving evaluated between each rTMS treatment session. An exploratory endpoint will be comparison of participant self-reported level of smoking the week prior to treatment with smoking 1 and 2 weeks after treatment, assessed by phone call.

5.0 Inclusion and Exclusion Criteria/ Study Population

• Patients will be screened for eligibility by brief phone interview and in person interview at study visit.

Inclusion Criteria

- Outpatient Adults aged 18-70
- Cigarette Smokers smoking at least 1 pack (20 cigarettes a day) with current smoking status confirmed by exhaled CO reading of >10ppm day of visit.
- Ability to provide informed consent

Exclusion Criteria

- Current treatment with varenicline or bupropion
- Currently making a smoking quit attempt (not currently smoking).
- Current treatment with an antidepressant, anti-convulsant, anxiolytic, antipsychotic or mood stabilizer.
- Current episode of major depression determined by MINI interview.
- Current or past history of schizophrenia, schizoaffective disorder, anorexia nervosa, bulimia or bipolar disorder as determined by MINI.
- Current daily consumption of alcohol or current alcohol use disorder.
- Current substance use disorder except for nicotine or cannabis use disorder.
- Currently pregnant or lactating.
- Contraindications to rTMS including history of seizure, metal implanted above the neck, pacemaker or any brain lesion.
- Unstable medical conditions
- Suicidal ideation or history of suicide attempt within the last six months.
- Inability or unwillingness of subject or legal guardian/representative to give informed consent

6.0 Number of Subjects

We plan to recruit 30 participants, 15 sham rTMS and 15 active rTMS

7.0 Setting

The study evaluation and intervention will take place at two locations. The first location is the Charleston Ralph H Johnson VA Medical Center in the outpatient brain stimulation clinic. The second location will be MUSC's brain stimulation facility at [name]. The same model of rTMS machine and coil will be used at both locations.

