8.0 Recruitment Methods

- Potential participants will be recruited from VA medical center clinics by distribution of fliers, and referral from providers. Additionally, study personnel may visit the VA smoking cessation group to provide information about the study to potential participants. We will also contact participants of other recent studies who provided consent to be contacted about future studies.
- Potential participants will be recruited by distribution of fliers, print advertisements, online craigslist advertisement and from MUSC internal medicine (UIM) clinic by distribution of fliers. Potential participants may be referred by clinicians. Additionally, we will contact participants of other recent studies who provided consent to be contacted about future studies.
- Compensation to study participants will be provided. Participants will receive \$20 for the study screening portion of the visit and \$120 if patient meets inclusion criteria and participates in the study.

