10.0 Study Design / Methods

The study will be a double blind, sham controlled design comparing cue induced nicotine craving before and after five sessions of active or sham rTMS. Participants will be recruited and will undergo a short phone screen to see if they qualify. The study will involve a single visit and participants will be asked to abstain from smoking or using nicotine replacement during the study visit. At the beginning of the visit study personnel will obtain informed consent from participants and confirm participants meet study inclusion criteria through administration of the MINI neuropsychiatric interview[22], review of current medications, medical history, urine pregnancy test if indicated and confirmation of smoking status by exhaled CO reading of >10ppm. The participants smoking history will be taken using the time line follow back and the Fagerstrom Test for Nicotine Dependence (FTND) will be administered to evaluate the severity of nicotine dependence[23]. Participants will be randomized to receive either sham rTMS or active rTMS. Participants cue induced nicotine craving will be evaluated before and the rTMS session. A week and 2 weeks after the participant's rTMS, they will be contacted by telephone and asked their current level of cigarette consumption.

rTMS treatments: rTMS will be delivered via a MagPro double blinded rTMS Research System (MagVenture, Denmark) with a Cool-B65 Butterfly Coil (a combined active and sham coil). We will use a standard resting motor threshold (rMT) determination to determine the TMS dose [24]. Treatment will be delivered at up to 110% resting motor threshold. Each active TMS session will consist of a total of 3000 pulses of 10Hz stimulation (5s-on,10s-off)[12]. Each treatment day will consist of 5 sessions of rTMS, each separated by approximately 30 minutes. A prior accelerated rTMS investigation has separated

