12.0 Data Management

Data will be managed using REDCAP and all data entry will take place directly into REDCAP in a deidentified manner, so that PHI will not be stored in REDCAP. A printed key linking REDCAP participant number with the participant name and contact information will be kept in a locked filing cabinet at the study location (VA participant information will be locked in cabinet at the VA). The only required paper items will be the consent and HIPAA documents. There will however be emergency paper backups of the database should the database be unavailable for any reason. If data is collected on paper, the information will be immediately transferred to the REDCAP database, and the paper record will be kept in a locked filing cabinet.

Statistical Analysis:

In preliminary analyses, we will examine the change in craving from pre-treatment to post-treatment in both groups (active rTMS vs. sham rTMS), and will use an independent two-group t-test to evaluate the difference in magnitude of change between the two groups. In final analyses, we will fit a generalized linear model to examine the impact of active vs. sham treatment on the magnitude of change from pre- to post-treatment craving. We will control for baseline craving since it is expected to be a strong predictor of post-treatment craving and may be imbalanced between study groups.

The main objective of this pilot study is to establish feasibility and tolerability of the accelerated rTMS treatment, and to begin to explore the possible treatment effect. Therefore, we do not focus on statistical power for this project. We aim to recruit 15 patients per group, which will provide a good foundation for estimating likely effect size and planning future studies.

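### No stratification by site is specified and neither planned analysis includes site, which leaves a small, avoidable loss of precision in the craving estimate (minor)

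*Combined protocol and SAP*

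**What the plan says.** - **Sites.** Section 7.0: "The study evaluation and intervention will take place at two locations", a VA medical center clinic and a university brain stimulation facility. It adds that "The same model of rTMS machine and coil will be used at both locations".
- **Recruitment.** Section 8.0 gives two routes. For the VA: "Potential participants will be recruited from VA medical center clinics by distribution of fliers, and referral from providers", with possible visits to its smoking cessation group. For the university: "Potential participants will be recruited by distribution of fliers, print advertisements, online craigslist advertisement and from MUSC internal medicine (UIM) clinic by distribution of fliers". Fliers, clinician referral and contact with participants of other recent studies appear in both.
- **Allocation.** Section 6.0: "We plan to recruit 30 participants, 15 sham rTMS and 15 active rTMS". Section 10.0: "Participants will be randomized to receive either sham rTMS or active rTMS". No method, block size or stratification factor is given.
- **Analysis.** Under Statistical Analysis in Section 12.0, the preliminary analysis "will use an independent two-group t-test to evaluate the difference in magnitude of change between the two groups". The final analysis is a generalized linear model of the change in craving, for which the plan states: "We will control for baseline craving since it is expected to be a strong predictor of post-treatment craving". The same sentence gives possible imbalance between the groups as a further reason. Site is not mentioned.

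**The concern.** Site is known before randomisation and stands for several things at once: the population recruited, the staff and the room. The outcome is self-reported craving, which any of these could affect. Section 7.0 standardises only the model of machine and coil. One route may bring in people who attend a cessation group. Section 5.0 excludes those in a quit attempt only if they are not currently smoking, so attenders who still smoke can enter.

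The plan adjusts for baseline craving partly because it may be imbalanced. Site could be unbalanced for the same reason, and adjusting for baseline craving removes a site difference only as far as that difference acts through baseline craving. Section 12.0 presents the 15 per group as a basis for estimating an effect size and planning later studies. What is at stake is therefore the precision and readability of that single estimate.

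**Working it through.** The plan has no figure of its own to reproduce: it states no alpha, power, effect size or SD, and says that power is not its focus.

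**Inputs**
- From Section 6.0: 30 participants, 15 per arm.
- Assumed, because the documents are silent: a site split of 15/15 (or 20/10); a difference *s* between sites in mean craving change of 0.3, 0.5 or 1.0 SD, where SD is the within-site SD of change; participants are treated at the site whose route recruited them.

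**1. Standard error with site balanced or adjusted for**

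SE = SD × √(2/15) = 0.365 SD, so the variance is 0.1333.

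**2. Chance of a site imbalance when allocation is not stratified (arms fixed at 15/15)**

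The number X from one site in the active arm is hypergeometric.
- 15/15 sites: P(X ≤ 5 or X ≥ 10) = 2 × Σ C(15,x)² / C(30,15) for x = 0 to 5 = 2 × 11,099,510 / 155,117,520 = 0.143. This is 10 v 5 or worse, in either direction.
- 20/10 sites: the probability that the arms differ by 4 or more participants from the smaller site is 0.245.

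**3. What one such imbalance does to the realised estimate**

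Shift = *s* × (10/15 − 5/15) = 0.333*s*. For *s* = 0.3, 0.5 and 1.0 this is 0.10, 0.17 and 0.33 SD, or 0.27, 0.46 and 0.91 of the 0.365 SD in step 1. This is a tail case and has mean zero over allocations. Step 4 gives the average cost.

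**4. Average cost in precision (15/15 sites)**

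The SD of the between-arm difference in site proportion is 0.1857, and its square is 0.0345. Without stratification or a site term, variance = 0.1333 + 0.0345*s*².

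| *s* (SD) | SE as planned, if unstratified | SE with the fix | Fall in SE | Information lost, of 30 participants |
|---|---|---|---|---|
| 0.3 | √0.1364 = 0.369 | 0.365 | 1.1% | 0.7 |
| 0.5 | √0.1420 = 0.377 | 0.365 | 3.1% | 1.8 |
| 1.0 | √0.1678 = 0.410 | 0.365 | 10.9% | 6.2 |

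The last column is 30 × (1 − 0.1333 / planned variance).

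**5. Check by simulation** (6,000 runs per scenario, no treatment effect, baseline craving not simulated, two-sided 0.05 assumed)
- The SD of the estimate fell from 0.379 to 0.366 at *s* = 0.5 (3.4%) and from 0.404 to 0.361 at *s* = 1.0 (10.6%), in line with step 4.
- Unstratified t-test without site: mean estimate about 0; type I error 0.046 to 0.055 across *s* = 0, 0.5 and 1.0 and both site splits.
- Stratified allocation analysed without site: type I error about 0.030 (15/15) and 0.033 (20/10) at *s* = 1.0, so the test is conservative.
- Stratified with a site term and no site effect (15/15): SD of the estimate 0.3662, against 0.3658 without the term, so the precision loss is negligible.

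**The case against.** A reader might infer that randomisation is not stratified by site. The documents do not say so. Section 10.0 is silent on the method, and the fixed 15 and 15 in Section 6.0 may imply some restriction. The omission of site from both analyses stands either way.

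A reader might also infer that site imbalance biases or confounds the comparison. It does not. Under randomisation the estimate is unbiased over allocations, the usual standard error already carries the between-site variance, and simulated type I error stayed near 5%. Setting a 10 v 5 shift beside the standard error as if it were extra error would count that variance twice.

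Several features limit how far the sites can differ. The outcome is a same-day, within-person change, with baseline craving in the final model. Eligibility and equipment model are common, and recruitment partly overlaps. Nothing in the documents shows a site difference in craving change, and a difference of 1.0 SD would be large.

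Finally, the main objective is feasibility and tolerability. The Aim 1 endpoint in Section 3.0, the percentage completing all five sessions, is not a comparison of arms and is untouched.

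All of this stands, and it limits the point to a modest gain in precision. It does not remove the point, because the gain costs almost nothing and stratification cannot be added once participants are enrolled.

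**Conclusion.** The point holds as a minor one. The plan specifies no stratification by site and omits site from both analyses, although it runs at two sites with largely different recruitment sources. The consequence is lost precision and a harder reading of one small realised sample; the validity of the test is not affected. With modest site differences (0.3 to 0.5 SD) the loss is about 1% to 3% of the standard error, and it reaches about 11% only at 1.0 SD. These figures rest on an assumed site effect, an assumed equal site split and allocation that is in fact unstratified. The site difference that counts for the final model is the part left after adjustment for baseline craving, so the gain there could be smaller.

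**What to change.** - **Section 10.0:** state the randomisation method. Allocate 1:1 in permuted blocks within each site, from concealed lists.
- **Section 12.0:** add site as a fixed factor beside baseline craving in the final model. If allocation is stratified the term is needed, because omitting it makes the test conservative. The preliminary t-test would share that conservatism and is best read as descriptive.

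**Cost.** Two lists instead of one, and one degree of freedom (residual 27 to 26 in a model with intercept, treatment and baseline craving). Blocks do not guarantee exactly 15 and 15: an incomplete block of four can leave the arms two apart at a site, so up to four apart overall. If the sites do not differ, the precision loss is negligible.

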8.0 Recruitment Methods

- Potential participants will be recruited from VA medical center clinics by distribution of fliers, and referral from providers. Additionally, study personnel may visit the VA smoking cessation group to provide information about the study to potential participants. We will also contact participants of other recent studies who provided consent to be contacted about future studies.
- Potential participants will be recruited by distribution of fliers, print advertisements, online craigslist advertisement and from MUSC internal medicine (UIM) clinic by distribution of fliers. Potential participants may be referred by clinicians. Additionally, we will contact participants of other recent studies who provided consent to be contacted about future studies.
- Compensation to study participants will be provided. Participants will receive \$20 for the study screening portion of the visit and \$120 if patient meets inclusion criteria and participates in the study.

9.0 Consent Process

Study personnel will obtain informed consent at the beginning of the study visit. The informed consent form includes a detailed description of the study procedures, along with statements regarding participants' rights to withdraw from the procedure at any time without consequences. The informed consent form will be explained to subjects in easy-to-understand language, and subjects will be instructed to read the form carefully prior to signing it. Consent will be documented by the signature of the participant on the informed consent agreement, accompanied by the signature of the individual obtaining the consent. We will obtain consent in a private office at each location.

10.0 Study Design / Methods

The study will be a double blind, sham controlled design comparing cue induced nicotine craving before and after five sessions of active or sham rTMS. Participants will be recruited and will undergo a short phone screen to see if they qualify. The study will involve a single visit and participants will be asked to abstain from smoking or using nicotine replacement during the study visit. At the beginning of the visit study personnel will obtain informed consent from participants and confirm participants meet study inclusion criteria through administration of the MINI neuropsychiatric interview[22], review of current medications, medical history, urine pregnancy test if indicated and confirmation of smoking status by exhaled CO reading of >10ppm. The participants smoking history will be taken using the time line follow back and the Fagerstrom Test for Nicotine Dependence (FTND) will be administered to evaluate the severity of nicotine dependence[23]. Participants will be randomized to receive either sham rTMS or active rTMS. Participants cue induced nicotine craving will be evaluated before and the rTMS session. A week and 2 weeks after the participant's rTMS, they will be contacted by telephone and asked their current level of cigarette consumption.

rTMS treatments: rTMS will be delivered via a MagPro double blinded rTMS Research System (MagVenture, Denmark) with a Cool-B65 Butterfly Coil (a combined active and sham coil). We will use a standard resting motor threshold (rMT) determination to determine the TMS dose [24]. Treatment will be delivered at up to 110% resting motor threshold. Each active TMS session will consist of a total of 3000 pulses of 10Hz stimulation (5s-on,10s-off)[12]. Each treatment day will consist of 5 sessions of rTMS, each separated by approximately 30 minutes. A prior accelerated rTMS investigation has separated

sessions by only 15-20 minutes and was well tolerated [25]. Treatments will be delivered at the EEG coordinate for F3 (which approximates the left DLPFC), and will be found using the Beam-F3 method [26]. Sham sessions will be delivered using an electronic sham system consisting of a coil that mimics the appearance and sound of TMS, combined with a transcutaneous electrical nerve stimulation (TENS) device which produces a small electric stimulus mimicking the feeling of real TMS. This type of sham has been demonstrated to be indistinguishable from real TMS, has been well tolerated in [9, 18], and successfully used in other clinical trials[20, 21]. During the rTMS, participants will watch a video of smoking related images.

Cue Induced Craving Assessment:

Cue induced nicotine craving will be evaluated before and after rTMS with a previously validated cue induced craving paradigm[12]. The cue induced craving paradigm presents neutral control images and smoking cue images in blocks and we will evaluate craving between each block using a visual analog scale described below. Participants will be asked to bring their cigarettes to study visit and will be instructed to hold, but not smoke, a cigarette.

The blocks will include scenic images (such as mountains), neutral control images (such as a person holding a pen), and cigarette-smoking cue images (such as a person lighting a cigarette) presented in four blocks with craving evaluated between each block. Physical cues such as a pack of cigarettes may be used as well.

Craving will be evaluated using a modified QSU-B [27] questionnaire using a 0-100 computerized visual analog scale (or paper based scale if computer is not available) designed to assess craving. The 10 QSU-B questions include the following: 1) I have a desire for a cigarette right now; 2) Nothing would be better than smoking a cigarette right now; 3) If it were possible, I probably would smoke now; 4) I could control things better if I could smoke; 5) All I want right now is a cigarette; 6) I have an urge for a cigarette; 7) A cigarette would taste good now; 8) I would do almost anything for a cigarette now; 9) Smoking would make me less depressed; 10) I am going to smoke as soon as possible.

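### Does the lack of a named analysis set for Aim 2, and of a rule for people who stop before session 5, undermine the craving comparison?

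*Combined protocol and SAP*

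**What the plan says.** Aim 1 names its denominator. Section 3.0 (Study Endpoints) defines the endpoint as the "percent of participants starting the rTMS treatment who complete all 5 rTMS treatments in a single day", and Section 1.0 expects that "greater than 75% of participants who start the rTMS course will complete the 5 treatments". The plan therefore separates starters from completers and accepts that some will stop.

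Aim 2 has no such statement. Its timing appears in several forms:

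- Section 1.0 expects a "greater decrease in cue induced nicotine craving after a five session treatment course of active rTMS".
- Section 3.0 restates the aim as a "decrease in cue induced nicotine craving after 5 sessions of rTMS", then gives the endpoint as the "difference in 0-100 averaged pre and post treatment smoking cue induced cigarette craving scores".
- Section 10.0 opens by describing a design "comparing cue induced nicotine craving before and after five sessions of active or sham rTMS".
- Later in that section the visit sequence reads "Participants cue induced nicotine craving will be evaluated before and the rTMS session", with a word missing.
- Under Cue Induced Craving Assessment: "Cue induced nicotine craving will be evaluated before and after rTMS with a previously validated cue induced craving paradigm".

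The Statistical Analysis text in Section 12.0 compares the change in craving between arms, first by t-test and then by a generalized linear model that controls for baseline craving. It names no analysis set and does not mention missing post-treatment scores. It makes feasibility and tolerability the main objective, sets power aside, and expects 15 per group to support an effect-size estimate for later studies.

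**The concern.** The plan foresees early stopping in Aim 1 but does not say what happens to those people in Aim 2. The sentence that should fix the time of the post-treatment score is the one that is broken. Some sentences tie the score to five sessions and others only to treatment in general. For a person who stops after sessions 1 to 4, two comparisons then seem to fit the text: everyone with a post-treatment score, or five-session completers only.

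If both sets existed in the data, they would generally give different estimates, and nothing in the supplied text prevents the choice from being made after results are seen. Since the trial is meant to inform the effect size of a later study, it matters who enters that estimate.

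**Working it through.** **Timing.** The assessment paragraph in Section 10.0 supplies the missing word (after), and the opening sentence of the same section supplies the number of sessions (five). Sections 1.0 and 3.0 agree. The shorter before-and-after phrases read as shorthand for the same time point, and no sentence schedules an earlier score. What remains is silence about people who stop, not a contradiction.

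**How many could be affected.** The plan gives no dropout figure to reproduce. Inputs: 30 planned participants (Section 6.0), all assumed to start; 88% retention in a cited three-day accelerated course in another population (Section 2.0, Background); 95% and 98% are assumed alternatives.

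- Expected stoppers at 88%: 30 × 0.12 = 3.6.
- P(at least one stopper) = 1 − r³⁰: 0.978 at 88%, 0.785 at 95%, 0.455 at 98%.
- The smallest count above 75% of 30 is 23 (22.5 rounded up), so the Aim 1 hypothesis is compatible with at most 7 stoppers. From the binomial, P(7 or more) is about 6% at 88% and below 0.1% at 95%.

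**Case A: stoppers are not assessed.** A change score needs both measurements, so everyone with a change score is a completer. The two sets are identical: the difference is zero and the choice has no effect on the error rate.

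**Case B: every stopper is assessed.** Assume stopping is random and early scores have the same mean and spread as full-course scores. Both estimates then have the same expectation. With m₁ and m₂ completers of 15 per arm, the SD of the difference between the two estimates is √[(1/m₁ + 1/m₂) − 2/15], in units of the SD of change:

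| Completers | SD of difference | 95% range (× 1.96) |
|---|---|---|
| 14 v 14 | √0.00952 = 0.098 | ±0.19 |
| 13 v 13 | √0.02051 = 0.143 | ±0.28 |
| 11 v 12 | √0.04091 = 0.202 | ±0.40 |

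**Sampling error.** Half-width = t(0.975, n₁+n₂−2) × √(1/n₁ + 1/n₂), with a two-sided 5% level assumed because the plan states none:

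- 15 v 15: 2.048 × 0.365 = 0.75 SD
- 13 v 13: 2.064 × 0.392 = 0.81 SD
- 11 v 12: 2.080 × 0.417 = 0.87 SD

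**Free choice between sets.** With no true effect, simulation of 400,000 trials puts the chance that at least one set gives p < 0.05 at about 6.7% with two stoppers per arm and 7.3% with a 4/3 split, against 5% for one fixed set. These rates apply only in Case B.

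**Non-random stopping.** Leaving stoppers out moves an arm's mean by the share left out times the difference between stoppers and completers. With assumed differences, 3 of 15 at 0.5 SD gives 0.20 × 0.5 = 0.10 SD. The extreme of all 7 in one arm at 1.0 SD gives 0.467 × 1.0 = 0.47 SD. Both are below 0.75 SD.

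**What an early score would measure.** One session is 3000/50 = 60 trains of 15 seconds, or 15 minutes. With the 30-minute spacing counted start to start or end to start, each missed session shortens the visit by 30 or 45 minutes. An early score would follow 0.5 to 0.75 hour less abstinence after stopping at session 4, and 2 to 3 hours less after session 1. It would also follow a partial course, possibly during the intensity ramp described in Section 15.0.

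**The case for a change.** The best case for a change is that this is a single-visit trial: a score not taken before the person leaves cannot be recovered, so whether to take it has to be settled in advance. The remedy would be a few sentences and a couple of data fields. The effect-size estimate is a stated purpose of the sample, and its meaning depends on who is in it. At 88% retention at least one stopper is very likely. A person randomized who never starts treatment is also left unplaced.

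Much of this stands. The text is silent, and stating a set in advance is good practice. It does not show that the plan would mislead. The documents give no sign that scores will be lost or that loss would differ by arm. The 88% comes from a three-day, 54,000-pulse course, whereas this is one day and 15,000 pulses. The inflated error rate needs stoppers to be assessed and an analyst to report whichever set looks better; the plan calls for neither. Early scores would not be a clear gain either, since they measure a partial course under shorter abstinence. Some of the numbered sections are absent from the supplied text, so the silence can be asserted only for what was supplied.

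**Conclusion.** No change to the plan follows. The broken sentence is a clerical slip that Section 10.0 itself resolves. The missing analysis set is a gap that an analyst would ordinarily fill by comparing everyone with both scores by assigned arm, reporting how many lack a post-treatment score, and showing completers separately if the two groups differ.

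If stoppers are not assessed, the two readings coincide. If all are assessed and stopping is random, they differ within ±0.19 to ±0.28 SD for one or two stoppers per arm, roughly a quarter to just over a third of the 0.75 SD half-width at 15 per arm. The ±0.40 SD figure needs seven stoppers, which has about a 6% chance of being reached or exceeded even at 88% retention.

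These figures assume that all 30 start and that change scores have equal spread in both arms; the documents give no SD, effect size or significance level. Aim 2 is exploratory, the plan makes no power claim, and the main objective has its own defined denominator.
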